4.2 EXCLUSION CRITERIA

1. Evidence of critical illness, defined by at least one of the following:
 - Respiratory failure defined based on resource utilization requiring at least one of the following: endotracheal intubation and mechanical ventilation, ECMO, or clinical diagnosis of severe acute respiratory distress syndrome with $\text{PaO}_2^*/\text{FiO}_2 \leq 100$.
*In case a direct measure of PaO_2 has not been obtained, it should be imputed according to a referenced formula (Ellis or Rice) ([Appendix 5 - Imputation of \$\text{PaO}_2/\text{FiO}_2\$ ratio](#)). For sites located over 1000 m altitude above sea level, $\text{PaO}_2/\text{FiO}_2$ ratio will be adjusted ([Appendix 6- Adjustment of \$\text{PaO}_2\$ from a Site at High Altitude](#); See also [Appendix 7](#) for FiO_2 imputations from oxygen flow rates).
 - Shock requiring vasopressors.
 - Multi-organ dysfunction/failure.
2. (Criterion eliminated and merged with inclusion criterion #4 based on AEMPS recommendations).
3. Any of the following cardiac conditions or risk factors:
 - Cardiac infarction or cardiac surgery episode within the last month;
 - History of known congenital QT prolongation;
 - Known structural cardiomyopathy with abnormal LVEF (<50%);
 - Current clinical evidence of heart failure or acute cardiac ischaemia (New York Heart Association (NYHA) class III-IV).
4. Hypersensitivity to the active ingredient or any of the excipients (mannitol, macrogolglycerol hydroxystearate, and ethanol) or contraindication to receive dexamethasone, antihistamine H1/H2, or anti-serotonergic 5HT₃ agents.
5. Females who are pregnant or breast-feeding.
6. Females and males with partners of childbearing potential (females who are not surgically sterile or postmenopausal defined as amenorrhoea for >12 months) who are not using at least 1 protocol-specified method of contraception.
7. Any situation currently requiring increasing needs of immune suppressive agents (e.g. acute graft rejection, flare of autoimmune disorder, or cytokine storm syndrome).
8. Any other clinically significant medical condition (including major surgery within the last 3 weeks before screening) or laboratory abnormality that, in the opinion of the investigator, would jeopardise the safety of the patient or potentially impact on patient compliance or the safety/efficacy observations in the study.
9. Participation in another clinical study involving an investigational drug within 30 days prior to screening.

5. PLAN OF THE STUDY

5.1 PLANNED TRIAL PERIODS (INDIVIDUALLY PER PATIENT)

Patients will be evaluated at scheduled visits:

- The Screening period: From the day patient has provided written informed consent to randomisation. The screening procedures should be preferably performed within 24 h prior to administration of study treatment, allowing a maximum of 48 h prior to administration of study treatment if required.
- The Treatment period: From Day 1 (date of randomisation) to 24 h after the last dose of the antiviral therapy. If no antiviral was given in the control arm, then the treatment period will finish on Day 4, for data management purposes. Antiviral treatment must always be started on the randomisation date.
- The Follow-up period: From the end-of-treatment until the end-of-study.
- The End of Study (EOS) is Day 60 (± 3) or date of early study termination unless ongoing SAEs, if applicable.

5.2 DISCONTINUATIONS

5.2.1 Screening Failure

Screen failures are defined as patients who consent to participate in the clinical study but are not subsequently randomised in the study. A minimal set of screen failure information is required to ensure transparent reporting of screen failure patients to meet the Consolidated Standards of Reporting Trials (CONSORT) publishing requirements and to respond to queries from regulatory authorities. Minimal information includes demography, screen failure details, eligibility criteria, and any SAEs related to the study participation. Rescreening is not allowed in this study.

5.2.2 Treatment Discontinuation

Treatment discontinuation occurs when an enrolled patient ceases to receive the study treatment regardless of the circumstances.

The primary reason for any treatment discontinuation will be recorded on the patient's electronic Case Report Form (e-CRF).

A subject may stop the study treatment but desirably should continue to the end of study. Should a patient decide to prematurely discontinue the study treatment (refuses treatment), all efforts will be made to complete and report the observations as thoroughly as possible. He/she should be asked if he/she can still be contacted for further information. The outcome of that discussion should be documented in the medical records. Whenever possible, patients who receive at least 1 dose of plitidepsin and withdraw from the study will be followed for at least 31 days (± 3 days) after administration of the last dose of plitidepsin to follow-up on possible open TEAEs at withdrawal or for potential late-onset treatment-related TEAEs.

Patients will receive the study treatment(s) while it is considered to be in their best interest. Specifically, individual treatment of a given patient will be prematurely ended if:

- Unacceptable toxicity despite allowed/applicable medical prophylaxis or therapy.
- Intercurrent illness of sufficient magnitude to preclude safe continuation of the study treatment.
- Patient's refusal (follow-up has to be continued for those patients who refuse treatment, but do not withdraw consent) and/or non-compliance with study requirements.
- A major protocol deviation that may affect the risk/benefit ratio for the participating patient.
- Investigator's decision.

A rapid disease progression per se is not an indication for treatment discontinuation and needs additional clinical input. Patients who are withdrawn for any reason must not be re-treated in the context of this study at any time.

All cases of treatment discontinuation must be documented (date and reason) in the eCRF. Patients will be informed that they have the right to withdraw from the study at any time, without prejudice to their medical care, and are not obliged to state their reasons.

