5.2.3 Study Discontinuation

Study discontinuation occurs when an enrolled patient ceases to participate in the study, regardless of the reason. Patients will remain on study until patient consent withdrawal, death, or the date of study termination (clinical cutoff) established by the Sponsor. The date and reason for study discontinuation will be clearly documented in the medical records of the patient.

If the patient withdraws consent for disclosure of future information, the Sponsor may retain and continue to use any data collected before such a withdrawal of consent. Additionally, patients may request destruction of any samples taken and not tested, and the investigator must document this in the site study records. Refer to the Schedule of Assessments ([Appendix 13](#)) for data to be collected at the time of study discontinuation and follow-up and for any further evaluations that need to be completed.

Reasons for study discontinuation can include, but are not limited to:

- Investigator's decision;
- Patient refusal as reason for discontinuation.

5.2.4 Lost to follow up.

A patient will be considered lost to follow-up if he/she repeatedly fails to return for scheduled visits on Days 8 (± 1), 15 (± 1), 30 (± 2), and 60 (± 3), and is unable to be contacted by the study site.

The following actions must be taken if a patient fails to return to the clinic for a required study visit:

- The site must attempt to contact the patient and reschedule the missed visit as soon as possible, counsel the patient on the importance of maintaining the assigned visit schedule, and ascertain whether or not the patient wishes to and/or should continue in the study.
- In cases in which the patient is deemed lost to follow-up, the investigator or designee must make every effort to regain contact with the patient (where possible, 3 telephone calls and, if necessary, a certified letter to the patient's last known mailing address or local equivalent methods). These contact attempts should be documented in the patient's medical record.

Should the patient continue to be unreachable, he/she will be considered to have withdrawn from the study with a primary reason of lost to follow-up.

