[¥]Antiviral treatment period in both arms will end 24 h after administration of the last dose of the antiviral therapy. If no antiviral was given in the control arm, then the treatment period will finish on Day 4.

[†]See [Section 7.2.1 Adverse Events of Special Interest \(AESIs\)](#).

For patients included in the study (all randomised patients) but never treated, only the applicable forms at baseline and off-study visit modules of the e-CRF should be completed but SAEs occurring during screening period need to be reported (using paper SAE forms).

All cases of treatment discontinuation must be documented (date and reason) in the electronic case report form (eCRF). A subject may stop the study treatment but desirably should continue follow-up to the end of study.

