6.1.4 Treatment Schedule and Dose

Plitidepsin will be administered as a 60-min (±5 min) IV infusion, every 24 h (±30 min)* for 3 consecutive days, at a dose of 2.5 mg.

For prevention of infusion-related (i.e., plitidepsin-related) reactions (IRRs), allergic reactions and emesis reactions, administration of premedications is mandatory in the experimental arms.

*Treatment windows do not apply for the first 30 patients enrolled in this study (experimental arm) who will be included in the pharmacokinetics evaluations.

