8.5 SUMMARY OF ESTIMANDS AND STATISTICAL TESTS

The primary estimand corresponding to the primary endpoint is defined as:

Treatment: Participants will be randomised to receive plitidepsin versus control in each group.

Population: Participants as defined through the inclusion and exclusion criteria, who have been randomised to the trial and who have taken at least 1 dose of study treatment (plitidepsin or control).

Variable:

–1-month all-cause mortality rate (Day 30 since randomisation).

Intercurrent events:

–The participant's data are collected and included in the analysis without regard for treatment discontinuation (treatment-policy strategy).

–In the event of the participant initiating another non-protocol therapy, 1-month all-cause mortality rate will be evaluated regardless of initiation of new non-protocol therapy (treatment-policy strategy).

Population level summary: the posterior probability associated for the odds ratio of 1-month all-cause mortality rate from a Bayesian logistic regression for each group comparison.

Below a summary table where main/supportive analyses are described. P values except for the primary analysis have to be considered as exploratory and nominal values will be shown.

Endpoints	Analyses
Efficacy primary endpoint	
1-month all-cause mortality rate.	
 -Bayesian odds ratio (primary analysis by CHBM) -Bayesian odds ratio (Berry's Method) - Unstratified odds ratio (Univariate Logistic regression) - Stratified odds ratio (Multivariate Logistic regression)
Key secondary endpoint	
Time to confirmed negativisation in SARS-CoV-2 antigen test or RT-PCR Ct > 30.	
 -Kaplan-Meier (unstratified and stratified) -Cox regression (unstratified and stratified)
Efficacy secondary endpoints	
Time to sustained end of COVID-related hospital care from the time of randomisation. Sustained discharge is defined as no subsequent admission within 30 days of initial end of hospital care [up to day 60 (± 3)], related to either COVID-19 or COVID-19 therapy	
 -Kaplan-Meier (unstratified) -Cox regression (unstratified)
Time to sustained improvement (defined in Section 7.1.3) and resolution of selected COVID signs/symptoms (See Appendix 10 - COVID-19 signs/symptoms checklist).	
 -Kaplan-Meier (unstratified) -Cox regression (unstratified)

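### Section 5.2.2 specifies follow-up after study withdrawal only for plitidepsin-dosed patients, which risks an arm imbalance in known Day-30 survival and in adverse events to about Day 34, of unknown size and direction

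*Protocol*

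**What the plan says.** **The one-arm rule.** Protocol 5.2.2 states, qualified by a condition of feasibility, that "patients who receive at least 1 dose of plitidepsin and withdraw from the study will be followed for at least 31 days". An allowance of three days either side applies. The clock starts at the last plitidepsin dose and the stated purpose is drug safety: events unresolved when the patient leaves, and delayed ones attributed to the drug. Neither document, as available, has a counterpart for a control who withdraws.

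**Who is counted.** The FAS (Protocol 8.2.1, SAP 8.6.2.1) requires survival follow-up to Day 30 (±2), or death. Under Protocol 5.4, accrual in each group continues until the target number of evaluable FAS patients is reached. The primary estimand (Protocol 8.5) wants data "included in the analysis without regard for treatment discontinuation (treatment-policy strategy").

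**When follow-up may end.** The statements differ in strength:
- 5.2.2, for patients who refuse treatment: "follow-up has to be continued for those patients who refuse treatment, but do not withdraw consent".
- 5.7: "A subject may stop the study treatment but desirably should continue follow-up to the end of study". Section 5.2.2 has similar wording.
- 5.2.3: "Patients will remain on study until patient consent withdrawal, death, or the date of study termination". The same section then lists, as reasons for leaving the study, the investigator's decision and "Patient refusal as reason for discontinuation".

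**The concern.** In an open-label comparison of mortality under a treatment-policy strategy, vital status has to be sought equally hard in both arms. Here the one explicit instruction to keep contact after study withdrawal applies to one arm, and its window happens to span the primary endpoint. It was written for adverse events, but a contact made for that purpose also shows whether the patient is alive.

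Because FAS membership depends on Day-30 status, unequal contact can become unequal inclusion. Known deaths count in both arms, whereas withdrawn survivors may be counted in one arm only. If the controls who leave have a good prognosis, control mortality is overstated. If they have a poor prognosis and their deaths go unseen, it is understated. Continued accrual replaces lost controls in number but does not undo the selection. Adverse events after withdrawal could likewise be captured for longer on plitidepsin.

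The loose exit rules in 5.2.2, 5.2.3 and 5.7 name no arm and do not create the imbalance. They do widen the route by which follow-up can end without withdrawal of consent.

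**Working it through.** The 31 days is a follow-up rule and not a derived figure, so there is nothing to reproduce. Two checks apply.

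**1. Calendar.** Plitidepsin is given daily "for 3 consecutive days, at a dose of 2.5 mg" (Protocol 6.1.4), with Day 1 the day of randomisation. The rule ends on the day of the last dose + 31 (±3).

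| Last dose | Rule ends | Range |
|---|---|---|
| Day 1 | Day 32 | 29 to 35 |
| Day 2 | Day 33 | 30 to 36 |
| Day 3 | Day 34 | 31 to 37 |

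Every row reaches the Day 28 to 32 survival window. For a last dose on Day 3, the time added after withdrawal is 34 minus the withdrawal day: 29 days if the patient leaves on Day 5, 14 on Day 20, 5 on Day 29, and none from Day 34 (Day 37 at most). After that the rule asks for nothing in either arm, although adverse events are collected to Day 60.

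**2. Size of a possible distortion.** Inputs:
- From the documents: 20 patients per arm in each randomised group, and 20% control mortality (Protocol 8.1).
- Assumed, because the documents give no values: no treatment effect; the same withdrawal proportion w in both arms (5%, 10% or 20%); full retrieval of Day-30 status on plitidepsin and none in controls; Day-30 mortality m among those who withdraw, between 5% and 40%.

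Controls with unknown status = 20w, that is 1, 2 or 4 of 20. Plitidepsin patients with unknown status = 0.

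Observed control mortality = (0.20 - w × m) / (1 - w). Observed plitidepsin mortality = 0.20.

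| w | m | Control mortality | Control minus plitidepsin |
|---|---|---|---|
| 5% | 5% | 0.1975/0.95 = 20.8% | +0.8 points |
| 5% | 40% | 0.180/0.95 = 18.9% | -1.1 points |
| 10% | 5% | 0.195/0.90 = 21.7% | +1.7 points |
| 10% | 20% | 0.180/0.90 = 20.0% | 0 |
| 10% | 40% | 0.160/0.90 = 17.8% | -2.2 points |
| 20% | 5% | 0.190/0.80 = 23.75% | +3.75 points |
| 20% | 40% | 0.120/0.80 = 15.0% | -5.0 points |

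The planned difference is 20% - 7.5% = 12.5 points. If the rule retrieves no one on plitidepsin, both arms lose the same number and the difference is 0 in every row.

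**Death imputation.** SAP 9.0 imputes death when information is lost before Day 28, for patients who stop treatment because of adverse events. If that were applied to every missing control, mortality would be 0.20 - w × m + w. At w = 10% this gives a difference of +6.0 (m = 40%) to +9.5 points (m = 5%). It is an upper bound, since the imputation is stated only for that subset.

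**The case against.** **The sentence is a drug-safety provision.** It is aimed at treatment-emergent events and holds only where possible, so assuming that it retrieves every plitidepsin withdrawer is generous. That stands, and the figures above are the extreme case.

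**Other rules cover both arms.** Early-termination procedures include survival status and adverse events (Protocol 3 and 5.9). Contact attempts precede a declaration of loss to follow-up (5.2.4). Adverse events are collected to Day 60 (7.4.1), and serious events are followed to resolution and are reportable even after a patient is off study (7.4.2). Section 5.2.3 also points to Appendix 13, which is not in the available text. So a reader who infers that a control's data simply stop at withdrawal goes too far. Still, none of the rules that can be read clearly requires a vital-status contact at Day 30 for a control who has already left.

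**Stronger readings that the documents do not support.**
- *That dosed patients get 31 more days after withdrawing.* The count runs from the last dose.
- *That Day-30 status will be missing mainly in controls.* No withdrawal rates by arm are given. Controls may receive an approved antiviral and need hospital care, so a greater wish to leave is conjecture.
- *That the rule inflates the chance of a false go decision.* Take a single group of 20 v 20, no effect, an N(0,1) prior on the log odds ratio and a normal approximation with 0.5 added to each cell. At 20% mortality, losing 10% of surviving controls only raises the chance of passing the 65% cut-off from 0.28 to 0.35. Losing control deaths and survivors equally at 10%, which leaves mortality unbiased, already gives 0.31. Losing 20% of deaths and 10% of survivors gives 0.26, below the baseline. At 10% mortality, the baseline of 0.21 becomes 0.33 with survivors only and 0.30 with equal loss. Much of the rise at that mortality is therefore discreteness: 2 v 1 deaths gives a posterior probability of 0.638 at 20 v 20 and 0.651 at 19 v 20. SAP version 3.0 also produces no Bayesian output (11.6, 11.6.1), so the cut-off will not be applied.

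**Conclusion.** The point holds as a risk. The only explicit post-withdrawal follow-up is written for plitidepsin-dosed patients, its window covers Day 30, and the FAS depends on Day-30 status. This can produce unequal missing survival status, and unequal capture of adverse events up to about Day 34 (Day 37 at most). Size and direction are unknown. At 10% withdrawal with full retrieval on plitidepsin only, the distortion is about -2.2 to +1.7 points. It is zero if those who leave have average prognosis or if the rule retrieves no one.

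Early closure makes the analysis descriptive (SAP 6.0), but mortality is still tabulated in the FAS (SAP 11.8, Table 3) and the SAP expects readers to compare the arms numerically, so the issue stays relevant. It merits a cheap improvement. The evidence does not support calling it a defect that invalidates the primary comparison. Appendix 13 should be checked, since it might already supply an arm-neutral contact.

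**What to change.** 1. Reword the 5.2.2 sentence to cover all randomised patients in both arms, counted from randomisation. For anyone who stops treatment or leaves the study, obtain vital status at Day 30 and serious adverse events over the same window, by phone or medical record, unless consent to this is refused. Keep the existing drug-safety follow-up for plitidepsin alongside it.
2. Reconcile 5.2.2, 5.2.3 and 5.7 so that they say the same thing about when follow-up, as distinct from treatment, may end.
3. In the abbreviated report, show by arm the number of withdrawals, their timing and the number with unknown Day-30 status. Since recruitment has closed, this is the step that still helps every reader. The wording changes matter for any patient still in follow-up and for reuse of the protocol.

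The cost is consent wording and a few extra calls or record checks in controls who withdraw. No visits are added.

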5.2.3 Study Discontinuation

Study discontinuation occurs when an enrolled patient ceases to participate in the study, regardless of the reason. Patients will remain on study until patient consent withdrawal, death, or the date of study termination (clinical cutoff) established by the Sponsor. The date and reason for study discontinuation will be clearly documented in the medical records of the patient.

If the patient withdraws consent for disclosure of future information, the Sponsor may retain and continue to use any data collected before such a withdrawal of consent. Additionally, patients may request destruction of any samples taken and not tested, and the investigator must document this in the site study records. Refer to the Schedule of Assessments ([Appendix 13](#)) for data to be collected at the time of study discontinuation and follow-up and for any further evaluations that need to be completed.

Reasons for study discontinuation can include, but are not limited to:

- Investigator's decision;
- Patient refusal as reason for discontinuation.

5.2.4 Lost to follow up.

A patient will be considered lost to follow-up if he/she repeatedly fails to return for scheduled visits on Days 8 (± 1), 15 (± 1), 30 (± 2), and 60 (± 3), and is unable to be contacted by the study site.

The following actions must be taken if a patient fails to return to the clinic for a required study visit:

- The site must attempt to contact the patient and reschedule the missed visit as soon as possible, counsel the patient on the importance of maintaining the assigned visit schedule, and ascertain whether or not the patient wishes to and/or should continue in the study.
- In cases in which the patient is deemed lost to follow-up, the investigator or designee must make every effort to regain contact with the patient (where possible, 3 telephone calls and, if necessary, a certified letter to the patient's last known mailing address or local equivalent methods). These contact attempts should be documented in the patient's medical record.

Should the patient continue to be unreachable, he/she will be considered to have withdrawn from the study with a primary reason of lost to follow-up.

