3.1 PRIMARY ENDPOINT

- *Efficacy primary endpoint*
 - 1-month[†] all-cause mortality rate. [†](Day 30 since randomisation).

3.2 KEY SECONDARY ENDPOINT.

- Time to confirmed negativisation in SARS-CoV-2 antigen test or RT-PCR Ct > 30.

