8.2 ANALYSIS POPULATIONS

8.2.1 Full Analysis Set (FAS) Population

All randomised patients who have taken at least 1 dose of study treatment (plitidepsin or control) and have completed follow-up for survival until day 30 (± 2). Patients who die before the end of follow-up period will also be included in the FAS population. FAS population will be analysed according to their randomised treatment arm.

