8.3 Endpoints

Efficacy primary endpoint:

- 1-month† all-cause mortality rate. †(Day 30 since randomisation).

Key secondary endpoint:

- Time to confirmed negativisation in SARS-CoV-2 antigen test or RT-PCR Ct > 30.

Secondary endpoints:

Efficacy secondary endpoints

- Time to sustained end of COVID-related hospital care from the time of randomisation. Sustained discharge is defined as no subsequent admission within 30 days of initial end of hospital care [up to day 60 (± 3)], related to either COVID-19 or COVID-19 therapy.
- Time to sustained improvement (defined in Protocol Section 7.1.3) and resolution of selected COVID signs/symptoms (See Protocol Appendix 10 - COVID-19 signs/symptoms checklist).
- Distribution of patients according to their clinical status by the 11-category WHO Clinical Progression Scale, at Days 4 (± 1), 8 (± 1), 15 (± 1), 30 (± 2), and 60 (± 3) (See Protocol Appendix 1 – 11-Point World Health Organization (WHO) Clinical Progression Scale).
- Percentage of patients requiring oxygen therapy on Days 4 (± 1), 8 (± 1), 15 (± 1), 30 (± 2), and 60 (± 3).
- Time to sustained discontinuation (i.e., at least 7 days) of oxygen supplementation.

Safety secondary endpoints

Frequency of the following events (all-cause and drug-related):

- Treatment-emergent adverse events (TEAEs);
- TEAEs \geq grade 3 according to the National Cancer Institute [NCI]-Common Terminology Criteria for AEs (CTCAE v.5.0);
- Adverse events of special interest (AESIs);
- Serious adverse events (SAEs);
- Drug related Serious Adverse Events (i.e., SARs);
- Adverse events leading to treatment discontinuation; and
- Deaths (COVID-19-related/all).
- Change respect to baseline* in individual study-defined laboratory parameters (See Protocol Section 5.7, 5.8 and 5.9 and Protocol Appendix 8 – Clinical Laboratory Analyses).
- Change respect to baseline* in individual vital signs (See Protocol Section 5.7, 5.8 and 5.9).

*Baseline = latest test performed between screening and drug administration

Other Secondary/Exploratory Endpoints

- Percentage of patients requiring advanced oxygen support on Days 4 (± 1), 8 (± 1), 15 (± 1), 30 (± 2) and 60 (± 3).
- Time to intensification of respiratory support (WHO >5) (See Protocol Appendix 1 – 11-Point World Health Organization (WHO) Clinical Progression Scale).
- Total duration of advanced oxygen support.
- Percentage of patients requiring high-flow oxygen on Days 4 (± 1), 8 (± 1), 15 (± 1), 30 (± 2), and 60 (± 3).

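### A post-discharge death that the site never learns of can leave the Day-30 mortality rate, because tracing is aimed at the patient and the FAS requires completed survival follow-up

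*Protocol*

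**What the plan says.** **Endpoint.** The primary endpoint is the "all-cause mortality rate" at Day 30 from randomisation (Protocol 3.1; SAP 8.3).

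**Tracing.** For a patient deemed lost, Protocol 5.2.4 puts this duty on the site: "must make every effort to regain contact with the patient (where possible, 3 telephone calls and, if necessary, a certified letter". The last known address is used for the letter, and local equivalents are allowed. If that fails: "Should the patient continue to be unreachable, he/she will be considered to have withdrawn from the study", with loss to follow-up as the primary reason.

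**Analysis set.** Protocol 8.2.1 and SAP 8.6.2.1 define the FAS as randomised, dosed patients who "have completed follow-up for survival until day 30" (±2). They add: "Patients who die before the end of follow-up period will also be included in the FAS population".

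**Missing status.** SAP 9.0 leaves missing values out by default. Its one relevant exception imputes death for patients who discontinue treatment because of adverse events and whose information is lost before Day 28.

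**Estimand.** Protocol 8.5 and SAP 11.6.1 define the population as randomised patients with at least one dose. They set no Day-30 completion condition.

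**Current analysis.** After early closure, SAP 11.6 and Table 3 report the primary endpoint as descriptive frequencies in the FAS. No Bayesian output is planned.

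**The concern.** When the endpoint is death, being unreachable can be a consequence of the outcome. Day-hospital patients are eligible (Protocol 4.1, criterion 4) and time to sustained end of hospital care is an endpoint (Protocol 3.3.1), so some patients will be at home well before Day 30. If one of them dies and nobody tells the site, the steps named in 5.2.4 may produce silence, and the plan then files the patient as withdrawn.

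At stake is the primary result. Such a patient is neither a known death nor a completed survivor, so the arm's rate is computed without them and is too low. The loss would also have been hard to see: Protocol 5.4 continues accrual until the target number of evaluable FAS patients is reached, so the planned count would be topped up.

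**Working it through.** The plan states no figure that depends on this point, so there is nothing to reproduce. The check has two parts.

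**1. Trace one patient through the rules.** Take a patient who completes treatment, goes home, dies on some day before Day 30, and whose death is not reported.

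| Rule | Does it catch the death? |
|---|---|
| Protocol 5.2.4, tracing | Only if a call, letter or local equivalent happens to reach someone who knows. No relative, physician, record or register is named |
| Protocol 5.2.4, closure | Patient classed as withdrawn |
| FAS, completed survival follow-up | Not met |
| FAS, death before end of follow-up | Met only if the death becomes known |
| SAP 9.0, default | No imputation |
| SAP 9.0, exception | Not applicable: treatment was not stopped for an adverse event |

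Result: the patient is in neither numerator nor denominator.

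Two further inconsistencies appear along the way.
- A patient who is covered by the SAP 9.0 exception still does not fit the FAS wording, since follow-up was not completed and the death is imputed, not observed. SAP 8.6.2.1 and 9.0 need reconciling.
- Protocol 5.2.2 asks, where possible, for at least 31 (±3) days of follow-up after the last dose in patients given plitidepsin who withdraw. With the third dose on Day 3, that reaches Day 3 + 31 = 34, or Day 3 + 28 = 31 at the short end, so it spans Day 30. No equivalent is stated for control patients.

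**2. Illustrate the size.** Inputs: 20 per arm and 20% mortality (Protocol 8.1), so 0.20 × 20 = 4 deaths. The number of missed deaths m is my assumption, ranged over 0 to 2, because the documents give no loss rate. Observed rate = (4 − m)/(20 − m).

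- m = 0: 4/20 = 20.0%
- m = 1: 3/19 = 15.8%
- m = 2: 2/18 = 11.1%

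If the same patients stay in the denominator and bounds are shown, m = 1 gives 3/20 = 15.0% to 4/20 = 20.0%, and m = 2 gives 2/20 = 10.0% to 4/20 = 20.0%. The true rate then lies inside the reported range.

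**Direction, on the originally planned scale.** This uses a single basket with no borrowing, an N(0,1) prior on the log odds ratio and an assumed N(0,10²) prior on the control logit. It is not the planned hierarchical model. The planned cut-off was 65%.

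| Observed plitidepsin | Observed control | Probability of superiority |
|---|---|---|
| 4/20 | 4/20 | 0.50 |
| 3/19 (one death missed) | 4/20 | 0.61 |
| 2/18 (two missed) | 4/20 | 0.72 |
| 2/20 | 4/20 | 0.75 |
| 2/20 | 3/19 (one missed) | 0.66 |
| 2/20 | 2/18 (two missed) | 0.53 |

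Missed plitidepsin deaths flatter the drug; missed control deaths count against it.

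**The case against.** The documents contain more safeguards than 5.2.4 alone suggests.

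- The duty is to make every effort, and local equivalent methods are allowed. A call or letter to the home may reach a relative.
- Survival status is listed in the follow-up and end-of-study tables (Protocol 5.8, 5.9). Day of death is recorded to Day 60 (7.1.4), caregivers may report adverse events (7.2), and SAEs are collected to Day 60 or death (7.4.2).
- Protocol 5.2.3 refers to Appendix 13 for data collected at discontinuation. That appendix is not in the supplied text, so a vital-status step there cannot be excluded.
- The FAS does not bar a death learned of late.
- The SAP imputes death for one class of lost patients.
- The study has closed, and the formal comparison has been dropped.

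Most of this stands as a limit on the claim, but it does not close the gap. The tracing duty is to regain contact with the patient, not to establish vital status. None of the other sources is tied to 5.2.4, and the survival-status row in 5.8 is timed to the treatment period. The imputation covers only patients who stopped for adverse events. Closure leaves the Day-30 FAS rate as the reported primary result.

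A reader might infer that the withdrawal label itself removes deaths. It does not: removal comes from the FAS completion condition together with the no-imputation default, so rewording 5.2.4 alone would still drop every patient whose status stays unknown.

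**Conclusion.** The concern holds in a limited form. Followed as written, the plan can drop an unlearned post-discharge death from the primary Day-30 mortality rate, and its stated follow-up after withdrawal is not the same in both arms. The FAS is also narrower than the plan's own estimand population.

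The size cannot be derived. The 15.8% and 11.1% figures rest on assumed losses of one and two deaths, all in one arm of 20 at 20% mortality. A reader might set the shift of 20.0 − 11.1 = 8.9 points against the targeted 12.5-point reduction. That would require half the deaths in one arm to be missed and none in the other, and nothing in the documents supports such a loss. Nor do they support saying that the bias favours plitidepsin, or that any death has in fact been missed. The 65% cut-off no longer applies, so the practical effect is on the descriptive rates.

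**What to change.** **Tracing (Protocol 5.2.4).** Before a patient is closed as lost, require Day-30 and Day-60 vital status to be sought in both arms from relatives or caregivers, the treating or primary-care physician, hospital records and, where consent and local law allow, a death register. Count any death found in the FAS at its date.

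**Analysis (SAP 8.6.2.1 and 9.0).** Keep all randomised and dosed patients in the primary set, as the estimand already states. Reconcile the FAS definition with the death-imputation rule so that one rule covers unknown status. Report the number with unknown Day-30 status by arm, with best-case and worst-case rates.

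**Timing.** Recruitment has ended, so apply the tracing now to any patient lost before Day 30, using existing contacts and records. A contact-person field collected at consent is an option only for a future protocol.

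**Cost.** A SAP revision, a short instruction to sites, and a small amount of site work per lost patient. Local privacy rules may limit register look-up, so some statuses may stay unknown; the best-case and worst-case rates show how much that matters.
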